7. RESEARCH QUESTION AND OBJECTIVES

The overall objective of this study is to evaluate characteristics, vaccine utilization and outcomes among vaccinated subjects with IC conditions. The primary analysis will be conducted on subjects vaccinated with BNT162b2. A variety of subgroup analyses are planned, along with multiple sensitivity analyses that will test how variations in study design affect results.

Primary Objectives:

Aim 1: Describe profiles, vaccine utilization and resource use among subjects with IC conditions vaccinated with BNT162b2

Aim 2: Evaluate incidence rates of breakthrough infections among subjects with IC conditions fully vaccinated with BNT162b2

Aim 3: Evaluate the clinical presentation of vaccine breakthrough cases among subjects with IC conditions, including time to infection and severity of disease (hospitalization, mortality)

Secondary Objectives

Evaluate Aims 1, 2, 3 and HCRU/costs over time and stratified by relevant patient characteristics (eg, age), in specific IC conditions and by vaccination type (eg, any Mrna).

Exploratory Objective

Generate early estimates of the effectiveness of BNT162b2 in preventing COVID-19 infection, stratified by relevant patient characteristics (eg, age), in specific IC conditions.

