8. RESEARCH METHODS

8.1. Study design

This study will be a retrospective database analysis utilizing data sets within the HealthVerity database (Philadelphia, Pennsylvania) covering the time period 01 December 2018 through 08 July 2021 (or latest data available) to describe the characteristics of subjects with IC conditions vaccinated with BNT162b2 and to evaluate the incidence of SARS-CoV-2 breakthrough infections.

Study period: 01 December 2018 – 08 July 2021 (or latest data available)

Index identification period: 11 December 2020 – 08 July 2021 (or latest data available; inclusive)

Index date: The first record for a SARS-CoV-2 vaccine (primary analysis: BNT162b2; sensitivity analyses: any Mrna, any authorized vaccine) from a medical claim, pharmacy claim, or chargemaster record.

Baseline period: 12-month period prior to the index vaccination date

Follow-up period: Variable period beginning after the index date and continuing until the earliest of the following: end of the study or end of continuous insurance enrollment.

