Other baseline medication use	Patient Characteristics	HealthVerity Vaccine Data	Medications for pre-existing conditions per the Sentinel COVID-19 Natural History Master Protocol (eg, angiotensin converting enzyme inhibitors (ACE), angiotensin-receptor blockers (ARB)).
Vaccine utilization	Patient Characteristics	HealthVerity Vaccine Data	Patterns of uptake. The proportion of IC and non-IC patients who are partially and fully vaccinated with BNT162b2 (or any other vaccines), at different calendar months and follow-up periods (eg, 7 days post dose 2, 14 days post dose 2). Mean, median, minimum, and maximum time between receipt of the first and second dose of BNT162b2 (or any other vaccine)

Table 4. Breakthrough Cases Definition

Variable	Role	Data source(s)	Operational definition
Breakthrough SARS-CoV-2 infection	Outcome	HealthVerity Vaccine Data	Among patients who meet the definition of fully vaccinated, a breakthrough SARS-CoV-2 infection will be defined by evidence of a claim with a diagnosis code of U07.1 that occurs >14 days after the second vaccination date. The first claim with a diagnosis of COVID-19 after this time will be used to assess mean and median time from the second dose until the breakthrough case

PFIZER CONFIDENTIAL

Table 5. COVID-19 Healthcare resource use and Costs definitions

Variable	Role	Data source(s)	Operational definition
Emergency department (ED) visit	Outcome	HealthVerity Vaccine Data	An outpatient claim with a place of service = 23 that occurs after the breakthrough COVID-19 diagnosis date or at the same time/episode of care
Outpatient Hospital Visit	Outcome	HealthVerity Vaccine Data	An outpatient claim with a place of service = 22 or 19 or a standard billing code that begins with '13' that occurs after the breakthrough COVID-19 diagnosis date or at the same time/episode of care
Other Outpatient Visit (not ED, not hospital-based)	Outcome	HealthVerity Vaccine Data	An outpatient claim that does not meet the definition for an ED visit or Outpatient hospital visit.
Hospitalization	Outcome	HealthVerity Vaccine Data	A record from the chargemaster data with encounter type of Inpatient OR a series of claims (separated by no more than 2 days) with a place of service = 21 or standard billing codes that begin with '11' or '12' that occur after the breakthrough COVID-19 diagnosis or at the same time/episode of care 1 st admission and readmissions will be differentiated.

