8.7. Data analysis

Data analyses will follow extensive feasibility analyses aimed at determining whether a full study and the assessment of vaccine effectiveness are feasible, as illustrated below:

Study implementation approach

Characteristics of the IC, non-IC and total population (IC + non-IC) groups will be described. Descriptive statistics for continuous variables will include N (number of patients), mean, median, standard deviation, Q1, Q3, minimum, and maximum. Categorical variables will be described using frequency counts and percentages.

The incidence rate of breakthrough cases of SARS-CoV-2 infection will be determined based on the following:

- Among fully vaccinated patients, those who have a claim for COVID-19 (ICD-10-CM: U07.1) that occurs on or after >14 days following their second dose of an mRNA vaccine (or 1st dose of Johnson & Johnson) will be considered to have had a breakthrough event. The time from 14 days after the qualifying dose until the breakthrough event will be the person time at risk.

PFIZER CONFIDENTIAL

- Among fully vaccinated patients with no evidence of COVID-19 after their qualifying dose, the time from 14 days after the qualifying dose until the end of follow-up will be the person time at risk.

[figure not shown]
The incidence rate of breakthrough cases of SARS-CoV-2 infection will be calculated as the number of patients who experience the event divided by the observed time at risk, and reported per 100 person years. Poisson 95% confidence intervals will be reported for the incidence rates.

Absolute effect measures such as risk difference between non-IC and IC will be reported. Time period specific effect estimates (eg, at 6 months after vaccination) may be estimated if feasible. The characteristics of the breakthrough infections will be described, including clinical presentation and severity.

The primary analysis will describe results among the non-IC cohort and the IC cohort who are vaccinated with BNT162b2. Subgroup analyses will include results for clinically meaningful subgroups as defined by vaccination type, relevant patient characteristics (eg, age), and each IC condition as listed below:

- HIV/AIDS
- Solid malignancy
- Bone marrow transplant
- Organ transplant (excluding bone marrow)
- Rheumatologic/inflammatory
- Primary Immunodeficiencies
- Other immune condition
- CKD or ESRD
- Hematologic malignancy

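### Time to breakthrough is summarised only among cases, so it cannot be separated from length of follow-up and cannot support comparisons between cohorts, strata or data cuts

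*Combined protocol and SAP*

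**What the plan says.** Section 7 words Aim 3 as an evaluation of the clinical presentation of breakthrough cases in subjects with immunocompromising (IC) conditions, "including time to infection and severity of disease". Table 4 in section 8.3 defines a breakthrough as a U07.1 claim "that occurs >14 days after the second vaccination date" and states that the first such claim "will be used to assess mean and median time from the second dose until the breakthrough case". This is the only estimator given for time to infection.

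Section 8.1 makes follow-up a "Variable period beginning after the index date", "continuing until the earliest of the following: end of the study or end of continuous insurance enrollment". Index dates run from 11 December 2020 to 08 July 2021 or to the latest available data.

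Section 8.7 does count subjects without an event, for whom "the time from 14 days after the qualifying dose until the end of follow-up will be the person time at risk", but only as the denominator of the incidence rate. It mentions estimates for specific time periods as optional, without naming an estimator, and lists other techniques as exploratory. Neither is tied to time to infection. Section 8.9 does not list the issue as a limitation.

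**The concern.** A mean or median taken only over subjects whose event fell inside the observation window is conditional on that window. If events are rare and the hazard is roughly constant, event times among cases spread over the available time at risk. The summary then sits near half of that time plus the 14-day lead, whatever the level of risk.

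This matters because the plan puts such figures side by side. Section 8.7 describes results for the IC and non-IC cohorts and for subgroups by vaccine type, age and IC condition. The secondary objective repeats Aim 3 over time and by stratum. Section 8.7 also foresees rolling updates with monthly data cuts. A group vaccinated earlier, or enrolled for longer, would show a longer time to breakthrough at an identical hazard, and a reader could take that as more durable protection.

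**Working it through.** The plan states no figure to reproduce.

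**Inputs from the documents**
- Index window (8.1): 11 December 2020 to 08 July 2021 = 209 days.
- Start of risk (Table 4, 8.7): 14 days after the qualifying dose.

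**Assumptions (the documents give no figure)**
- 21 days between doses. The longest time from dose 2 is then 209 − 21 = 188 days, and the longest time at risk 188 − 14 = 174 days.
- Breakthrough rate between 0.5 and 20 per 100 person-years (PY).
- Constant hazard, except in step 4.

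**Formula.** For constant hazard λ and time at risk τ, the case-only mean counted from dose 2 is

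14 + 1/λ − τ·exp(−λτ)/(1 − exp(−λτ)),

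which tends to 14 + τ/2 when λτ is small. The median is 14 − ln(1 − F/2)/λ, with F = 1 − exp(−λτ).

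**1. Same follow-up (τ = 174 days), different risk**

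| Rate per 100 PY | Case-only mean (days) | Cumulative incidence |
|---|---|---|
| 0.5 | 101.0 | 0.24% |
| 1 | 100.9 | 0.48% |
| 10 | 100.3 | 4.65% |
| 20 | 99.6 | 9.09% |

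A 40-fold change in rate moves the mean by 1.4 days. Cumulative incidence separates the rates clearly.

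**2. Same risk (1 per 100 PY), different follow-up.** For τ = 60, 90, 120 and 174 days the mean is 44.0, 59.0, 74.0 and 100.9 days.

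**3. Two cohorts with staggered entry, same hazard (2 per 100 PY).** Let τ be uniform over 60-174 days in cohort A and 30-144 days in cohort B. For rare events the case-only mean at risk is close to E[τ²]/(2E[τ]).
- The variance of τ is 114²/12 = 1,083 in both cohorts.
- A: E[τ] = 117, E[τ²] = 117² + 1,083 = 14,772, and 14,772/234 = 63.1. With the lead, 77.1 days.
- B: E[τ] = 87, E[τ²] = 87² + 1,083 = 8,652, and 8,652/174 = 49.7. With the lead, 63.7 days.

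Numerical integration at 2 per 100 PY, without the rare-event approximation, gives:

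| | A | B | Gap |
|---|---|---|---|
| Mean (days) | 77.0 | 63.7 | 13.4 (before rounding) |
| Median (days) | 72.4 | 58.3 | 14.1 |

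The mean gap is 13.4 days at 0.5 per 100 PY and 13.1 at 20. Tripling the hazard in cohort B from 2 to 6 per 100 PY moves its mean only from 63.7 to 63.5 days.

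**4. Same follow-up (174 days), different hazard shape.** The mean is 100.9 days for a flat hazard, 118.2 if it rises 4-fold, 83.4 if it falls 4-fold and 76.9 if it falls 10-fold. The summary therefore does carry information on timing, but mixed with follow-up.

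**5. Later data cuts.** If cohort B is closed to new entrants and every subject is followed 30, 60 or 90 days longer at the same hazard, its mean goes from 63.7 to 77.0, 91.1 and 105.4 days.

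**The case against.** Aim 3 is worded about breakthrough cases, so a mean and median among cases answers it literally, and section 8.5 calls the study mainly descriptive. This stands: a labelled case-only description is legitimate, and what is missing is a censoring-aware complement and a caveat.

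The plan also handles censoring elsewhere. Incidence rates use the person-time of non-cases, the named contrast between IC and non-IC is a risk difference, follow-up time is a reported variable, and time from vaccination is listed as a potential confounder. No formal comparison of mean time to breakthrough is planned, so the harm depends on a reader comparing the figures informally. That is fair, but the plan reports them by cohort, by stratum and over time, which makes such a reading foreseeable. None of these elements corrects the summary itself.

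Two stronger readings are tempting. A reader might infer that the summary measures follow-up and nothing about how soon infections occur. Step 4 rules that out, because hazard shape alone moves the mean from 76.9 to 118.2 days at fixed follow-up. A reader might also infer that every monthly cut must lengthen it for all subjects. Section 8.1 does not support that: the index period may also extend to the latest data, so a cut can add recent vaccinees with short follow-up, and follow-up of disenrolled subjects does not grow.

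**Conclusion.** The point holds as a limited one. The only planned summary of time to infection barely responds to the level of risk and cannot be separated from follow-up length, so it cannot support comparison of IC with non-IC, of strata, or of successive data cuts. In the illustration, a 30-day shift in follow-up at an identical hazard produces a gap of about 13 days in the mean and 14 in the median. The near-constancy of the mean gap across rates shows that this does not hinge on the assumed rate. Its size in the real data depends on how far vaccination timing and enrollment differ between groups, which the documents do not give. Later cuts will tend to lengthen the summary where follow-up grows, unless new vaccinees offset this.

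The defect is confined to the time-to-infection element of Aim 3. It should be corrected before analysis, but it does not threaten the Aim 2 rates.

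**What to change.** In Table 4 and section 8.7:
- Add Kaplan-Meier cumulative incidence of breakthrough from day 14 after the qualifying dose, censored at end of follow-up, reported at fixed times separately for IC and non-IC.
- Add incidence rates by time since vaccination, for example 0-30, 31-60, 61-90 and more than 90 days at risk.
- Keep the case-only mean and median as a description of the cases, labelled as not comparable between cohorts or data cuts.
- State that these additions correct for unequal follow-up but not for calendar-time differences in exposure between early and late vaccinees, so a change with time since dose is not by itself evidence of waning.

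The dates needed (qualifying dose, first qualifying claim, end of follow-up) are already defined. The cost is a few sentences, a little extra analysis and one figure.

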Intensive Care Unit (ICU)	Outcome	HealthVerity Vaccine Data	A claim with a procedure code indicative of ICU utilization during a hospitalization that occurs after the breakthrough COVID-19 diagnosis or at the same time/episode of care 1 st admission and readmissions will be differentiated.
Invasive Mechanical Ventilation (IMV) / Extracorporeal Membrane Oxygenation (ECMO)	Outcome	HealthVerity Vaccine Data	A claim with a procedure code indicative of IMV/ECMO utilization during a hospitalization that occurs after the breakthrough COVID-19 diagnosis or at the same time/episode of care Includes both 1 st admission and readmissions.
Inpatient Death	Outcome	HealthVerity Vaccine Data	Death that occurs on or after the date of the breakthrough COVID-19 diagnosis. The date of death will be assumed to be the same as the date of the last recorded encounter in the database.

PFIZER CONFIDENTIAL

Table 5. COVID-19 Healthcare resource use and Costs definitions

Variable	Role	Data source(s)	Operational definition
			
Death information is available from the Charge Description Master (CDM) data and is provided as year-month of death only.
 
Time to death will also be explored.

Length of Stay (LOS)	Outcome	HealthVerity Vaccine Data	
Length of stay (LOS) associated with different types of hospitalization treatments mentioned above (eg, ICU), applicable for first index hospitalization and/or readmissions.

Costs	Outcome	HealthVerity Vaccine Data	
Non-zero costs associated with any of the previously listed Outpatient and Inpatient encounters (but death).
 
Charges may be assessed in sensitivity analyses to interpret the cost data.

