8.8. Quality control

Data in HealthVerity's COVID Healthcare database are collected weekly in an electronic format. HealthVerity employs its foundational product to match patients between different data sources with high accuracy. However, not all data points are available in every data source and as a result, not all variables in the database are completely populated. In addition, the database contains both pre- and post-adjudicated claims and, based on the data source, adjudication may or may not be captured. To maximize data completeness and uniformity, it may be necessary to exclude certain data sources from the analysis due to differences in data structure and content.

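### Table 5 defines outpatient care claim by claim, with no collapse to a visit and no precedence between ED and outpatient hospital, so one ED episode can count more than once and in more than one setting

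*Combined protocol and SAP*

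**What the plan says.** Table 5 in Section 8.3 has three outpatient rows.

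- **ED visit:** "An outpatient claim with a place of service = 23 that occurs after the breakthrough COVID-19 diagnosis date"; claims belonging to the episode in which the diagnosis was made also qualify.
- **Outpatient hospital visit:** "An outpatient claim with a place of service = 22 or 19 or a standard billing code that begins with '13", with the same timing condition.
- **Other outpatient visit:** "An outpatient claim that does not meet the definition for an ED visit or Outpatient hospital visit".

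The Hospitalization row is built differently. Where it relies on claims, it takes "a series of claims (separated by no more than 2 days) with a place of service = 21" (or certain inpatient billing codes), so several claims form one stay.

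The Costs row covers "Non-zero costs associated with any of the previously listed Outpatient and Inpatient encounters (but death"). It has no rule for allocating a cost to a setting or an episode.

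Section 8.8 adds that "the database contains both pre- and post-adjudicated claims and, based on the data source, adjudication may or may not be captured". Section 8.7 gives only generic descriptive summaries. It does not say whether resource use will be reported as visits per patient or as patients with at least one visit.

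**The concern.** A claim is a billing record and a visit is an event. The protocol respects that difference elsewhere: Section 8.2.1 asks for outpatient visits on different dates to establish an immunocompromising condition, Table 2 asks for the two vaccine claims to fall on different days, and the Hospitalization row merges neighbouring claims. The three outpatient rows have nothing similar.

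The reference to the same episode of care does not fill the gap. It fixes timing relative to the COVID-19 diagnosis and does not merge claims.

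The ED and outpatient hospital rows can also overlap. The outpatient hospital row accepts any 13x billing code without excluding ED care. A 13x claim that belongs to an ED episode is therefore an outpatient hospital visit, and a record that also carries place of service 23 meets both rows.

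Resource use is named in Aim 1, and HCRU and costs, over time and by subgroup, are a secondary objective. Table 5 is the only place where these outcomes are defined. Two programmers following it could report different visit counts and setting costs, and the difference would recur with each monthly data cut.

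**Working it through.** The plan states no visit count or cost, so there is no figure to reproduce. The check applies the three rows literally, claim by claim, to assumed ED episodes.

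**Inputs from Table 5.** ED: place of service (POS) 23. Outpatient hospital: POS 22 or 19, or a 13x billing code. Other: meets neither of those rows.

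**Assumed inputs.** The documents do not give the number or coding of claims in an ED episode. The range used is 1 to 3 claims at 1 cost unit each.

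**Formulas.**
- Visits = sum over claims of the number of rows each claim meets.
- ED cost share = cost of claims meeting the ED row ÷ cost of all claims in the episode.
- Cost ratio = sum of the row costs ÷ true episode cost.

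| Case | Claims in one ED episode | Visits (ED + hospital + other) | Settings | ED cost share | Cost ratio |
|---|---|---|---|---|---|
| A | one POS 23 | 1 + 0 + 0 = 1 | 1 | 1/1 = 100% | 1/1 = 100% |
| B | two POS 23 | 2 + 0 + 0 = 2 | 1 | 2/2 = 100% | 2/2 = 100% |
| C | POS 23; 13x | 1 + 1 + 0 = 2 | 2 | 1/2 = 50% | 2/2 = 100% |
| D | POS 23; 13x; another POS | 1 + 1 + 1 = 3 | 3 | 1/3 = 33% | 3/3 = 100% |
| E | one record with both POS 23 and 13x | 1 + 1 + 0 = 2 | 2 | 1/1 = 100% | (1 + 1)/1 = 200% |

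**Reading the table.**
- Case A is counted correctly. The other four give 2 or 3 visits for one episode.
- An indicator for any ED visit equals 1 in all five cases. An indicator for any outpatient hospital visit is switched on in C, D and E, and one for any other outpatient visit in D.
- Cost moves between settings in C and D, but the total is preserved in A to D. Only in E is cost counted twice.
- If mean cost per ED visit were reported, case B would give 2/2 = 1 unit per visit instead of 2/1 = 2.

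**After the change below.** If the claims of the episode share a date, each case gives 1 ED visit in 1 setting, with 100% of the cost under ED and a cost ratio of 100%.

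**The case against.** The strongest reply is that Table 5 gives criteria for recognising a type of care and does not promise to tally every qualifying claim. If the report shows patients with at least one ED visit, the main ED figure is untouched. That is right as far as it goes. But the plan does not choose that metric, the corresponding outpatient hospital and other outpatient proportions can still be inflated, and setting-specific costs depend on the row a claim lands in.

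The size also depends on a claim mix that the documents do not give, and at the low end (one claim per episode) there is no error. This stands, so the result is a range and the effect is possible, not certain.

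Several stronger readings are tempting, but the documents do not support them:

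- **No setting order at all.** The other outpatient row is a residual category, so a partial order exists. What is missing is an order between ED and outpatient hospital, and any order at episode level.
- **Every claim present twice because of adjudication.** Section 8.8 describes differences between data sources and allows sources to be excluded. It does not say that the same claim appears in two versions, so doubling the counts has no basis in the text.
- **Most of the ED cost booked elsewhere.** No document gives the share of an ED bill carried on a 13x claim.
- **A biased contrast between immunocompromised and other patients.** This would need more claims per episode in one cohort, which nothing in the documents shows. Proportional inflation in both cohorts would leave a ratio unchanged.
- **Damage to Aim 3 severity.** Aim 3 names hospitalization and mortality. The first has its own grouping rule, and the second is not a count of outpatient claims.

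**Conclusion.** The concern holds in a limited form. Table 5 sets the outpatient unit at the claim, gives no collapse to a visit, and leaves ED and outpatient hospital without precedence. Applied as written, it can count one ED episode more than once and place it, with its cost, in more than one setting.

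Under the assumed 1 to 3 equal-cost claims, one episode gives 1 to 3 visits in 1 to 3 settings, with 33% to 100% of its cost under ED. If a single record meets both rows, the setting costs sum to 200% of the true cost. Otherwise total cost is unchanged, and the proportion of patients with any ED visit is unchanged throughout.

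The effect is confined to descriptive resource use and setting-specific costs (Aim 1 and the secondary HCRU/cost objective). Breakthrough incidence rates and the hospitalization and mortality outcomes of Aim 3 do not depend on these rows. The point should be settled in the definitions before the resource-use tables are produced, but it does not threaten the main results.

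**What to change.** Amend Table 5 as follows:

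1. Collapse outpatient claims to one visit per patient per date.
2. Assign one setting to each patient-date, with ED ahead of outpatient hospital and outpatient hospital ahead of other. A 13x claim on the same date as a POS 23 claim then belongs to the ED visit.
3. Sum costs over all claims in the collapsed visit, counting each claim once.
4. Where a source holds more than one version of a claim, keep one: the adjudicated version if it is captured.

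The cost is definition wording and a little programming. Two genuinely separate visits on one date would count as one, with their costs together under the higher-ranked setting. An ED episode whose claims carry two dates would still count as two visits. Both limits should be stated with the results.

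### Aim 3 mortality has one named death source (chargemaster data) but no matching denominator, and the death-date rule can contradict the recorded month of death

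*Combined protocol and SAP*

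**What the plan says.** Aim 3 in section 7 is a primary aim. It covers the clinical presentation of breakthrough cases, "including time to infection and severity of disease (hospitalization, mortality". Section 8.7 plans to describe severity and to give results for the IC cohort, the non-IC cohort and each IC condition.

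The sources behind these results, all in section 8.3, are:

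- **Cases** (Table 4): among fully vaccinated patients, "a breakthrough SARS-CoV-2 infection will be defined by evidence of a claim with a diagnosis code of U07.1".
- **Hospitalizations** (Table 5): "A record from the chargemaster data with encounter type of Inpatient OR a series of claims (separated by no more than 2 days", with qualifying place-of-service or billing codes.
- **Deaths** (Table 5, Inpatient Death): "Death information is available from the Charge Description Master (CDM) data and is provided as year-month of death only". No other death source is named.
- **Definition of death** (same row): "Death that occurs on or after the date of the breakthrough COVID-19 diagnosis". Despite the row's label, the definition has no inpatient condition, cause or time limit.
- **Date of death** (same row): "The date of death will be assumed to be the same as the date of the last recorded encounter in the database". Time to death is to be explored.

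Section 8.2.1 requires 12 months of medical enrollment but no linkage to chargemaster data. Section 8.5 says feasibility work confirmed data on vaccination, IC conditions and breakthrough infections; deaths are not listed. Section 8.8 warns in general that "not all data points are available in every data source", and section 8.9 mentions differing missingness between sources. Neither mentions death.

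**The concern.** The numerator and the likely denominator of mortality come from different sources. On the plan's wording, a breakthrough case with no chargemaster data can enter the analysis, and can count as hospitalized, without any named route by which a death would be recorded. If such cases stay in the denominator, they are counted as survivors.

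The reported proportion then mixes mortality with chargemaster coverage. If coverage differs between IC and non-IC cases, or between IC groups, a mortality difference could be created, hidden or exaggerated by where patients were treated and how their stays were captured.

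The date rule is a separate and smaller matter. The source supplies the month of death, but the assigned date need not fall in that month.

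**Working it through.** The plan states no expected mortality, chargemaster coverage or sample size, so there is no figure to reproduce. All numerical inputs below are assumptions.

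**1. Effect on one proportion.** Let p be the true proportion who die and c the share of those deaths that carry a chargemaster death record. With all cases in the denominator, observed mortality = p × c, a relative understatement of 1 − c.

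- Hospitalized cases, assumed p = 10%: c = 0.2, 0.5, 0.8 gives 2%, 5%, 8%.
- All breakthrough cases, assumed p = 5%: c = 0.2, 0.4, 0.6, 0.8 gives 1%, 2%, 3%, 4%.

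**2. Effect on the IC versus non-IC comparison.** Assume true mortality of 10% (IC) and 5% (non-IC), so the ratio is 2.0 and the difference 5 points.

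| c, IC | c, non-IC | Observed IC | Observed non-IC | Ratio | Difference |
|---|---|---|---|---|---|
| 0.5 | 0.5 | 5% | 2.5% | 2.0 | 2.5 points |
| 0.4 | 0.8 | 4% | 4% | 1.0 | 0 points |
| 0.8 | 0.4 | 8% | 2% | 4.0 | 6 points |

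Equal coverage preserves the ratio but halves the difference here. Unequal coverage changes both, in either direction.

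**3. Effect of a matched denominator.** If deaths and denominator both come from stays with a chargemaster inpatient record, c drops out and an assumed 10% reads 10%. This estimates mortality in covered stays. It equals mortality in all stays only if covered and uncovered stays have the same mortality.

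**4. The date rule.** Suppose the last encounter is g days before death and deaths are spread evenly over a month of 30.4 days. The share of assigned dates falling in an earlier month than the recorded one is then about g / 30.4: 3 / 30.4 = 0.10 for 3 days and 7 / 30.4 = 0.23 for 7 days. A record dated after death would move the date the other way. By comparison, a mid-month date errs by at most about 15 days (standard deviation 30.4 / √12 = 8.8 days). The last-encounter rule has no stated bound.

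**5. The test that death follows the breakthrough.** If the breakthrough claim counts as a recorded encounter, the last encounter can never precede it. The rule then drops no recorded death, but it also cannot detect a record whose month of death is before the breakthrough. Section 8.9 allows that linkage may give one identifier to different people, so such conflicts are possible.

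**The case against.** The strongest objection is that two premises are inferred. In the Table 5 sentence, the word only limits the date to year and month; it does not say that chargemaster data are the sole source of deaths. Section 8.4 describes linked medical records, and linkage is by patient, so someone whose admission appears only in claims may still have chargemaster data. Nor is the mortality denominator stated, and section 8.8 lets the analysts exclude data sources for completeness. This stands. A reader might infer that a claims-only case can never be recorded as dead and that mortality is certainly understated; the documents do not go that far. They do name no other death source and restrict no denominator, and the general caveats do not repair that.

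It is also fair that nothing in the documents suggests coverage differs by IC status, that the study is mainly descriptive, and that no test of mortality is planned.

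On dates, a reader might infer that time to death is unreliable. For a true in-hospital death, the last encounter will usually be the terminal stay, so the error is probably small. A time of zero days is not necessarily wrong if diagnosis and death share an episode. The direction of any error is unknown, and time to death is exploratory.

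A reader might also infer from "A claim with a procedure code indicative of ICU utilization during a hospitalization" that ICU care, and likewise ventilation or ECMO, cannot be recorded for a chargemaster-only stay. The protocol uses the word claim loosely: section 8.1 takes the index vaccination from claims or chargemaster records, while section 8.2 calls it a vaccine claim. This needs only a clarification of wording.

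**Conclusion.** The concern holds in a limited form, and the plan should be changed. Mortality is a named part of a primary aim, its only named source is chargemaster data, and nothing ties the denominator to that source. If deaths are counted over all breakthrough or all hospitalized cases, mortality is likely understated by a factor equal to the share of deaths captured. IC versus non-IC mortality is distorted if that share differs between them.

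The size cannot be determined. Every percentage and ratio in the working rests on assumed mortality and coverage, and none should be read as an estimate for this study. The date rule can contradict the recorded month of death. That is a gap in specification with a probably modest effect, and it bears mainly on an exploratory result.

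**What to change.** In Table 5:

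1. Report in-hospital death among breakthrough hospitalizations that have a chargemaster inpatient record, and state that denominator. Label any figure over all cases as a lower bound.
2. Report the share of hospitalized breakthrough cases with chargemaster coverage for the IC cohort, the non-IC cohort and each IC group.
3. Require the assigned death date to fall in the recorded year and month. Use the end of the chargemaster stay in that month; failing that, the last encounter in that month; failing that, treat the date as interval-bounded by the month.
4. Flag deaths whose recorded month precedes the breakthrough.
5. Say whether chargemaster procedure records count for ICU care and for ventilation or ECMO.

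In section 8.9, name under-capture of deaths as a limitation.

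The work is revised wording and a source flag for each stay. The downside is a smaller mortality denominator, thin in some of the 12 IC groups and limited to hospitals with chargemaster data.
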